6.1.1. Total Cohort at Month X

The total cohort at Month X will include all vaccinated subjects from the vaccination stage of Study MenACWY-TT-027 (108658) who return for the Month X follow-up. The analysis of persistence will include all vaccinated subjects for whom data concerning persistence endpoint measures are available.

6.1.2. According-To-Protocol (ATP) Cohort for Persistence at Month X

Two ATP cohorts for persistence at Month X are defined, one for MenC and one for MenAWY. The requirements for both cohorts are the same except that membership in the MenC (or MenAWY) cohort requires at least one MenC (or MenAWY) titer.

The ATP cohort for persistence at Month X will include all evaluable subjects:

- who were eligible in Study MenACWY-TT-027 (108658).
- who received the primary vaccination with MenACWY-TT, Meningitec, or Mencevax ACWY during Study MenACWY-TT-027 (108658) according to their vaccine group.
- who have available assay results for at least 1 of 3 antigens (MenA or MenW-135 or MenY) or for MenC (for subjects who did not receive MenC vaccine because they were non-responders during the persistence phase of Study MenACWY-TT-027 please see Section 7.1 of the SAP) at Month X.

MenACWY-TT-100 (C0921004)

- who only received a meningococcal vaccine planned in Study MenACWY-TT-027 (108658) before Month X (with the exception of subjects who received the MenC vaccine because they were suboptimal responders during the persistence phase of Study MenACWY-TT-027).
- who did not have a history of meningococcal disease prior to Month X.
- who complied with the blood sampling intervals defined in the protocol for Month X (see Table 5 of the protocol and Table 2).
- who did not have an immune compromising medical condition.
- who did not receive any immunosuppressant(s) or other immune-modifying drug(s), immunoglobulins, any blood products, investigational drugs, and/or investigational vaccines within 30 days of the persistence blood sample.
- who were not excluded from the ATP cohort in the primary study (MenACWY-TT-027 [108658]) and from the previous ATP persistence cohorts, unless the reason for exclusion was either non-compliance with the protocol-defined serum sampling windows or a lack of availability of immunogenicity results at a previous time point.

Table 2. Intervals from Primary Vaccination in TT-027 to Persistence Visits

Visit	Interval in Days
78 months	2290-2458
90 months	2655-2823
102 months	3020-3188
114 months	3386-3554
126 months	3751-3919

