6.1. Persistence Cohorts

The requirements for the persistence cohorts are summarized in Table 1. Details are included in Section 6.1.1 through Section 6.1.4.

Table 1. Summary Description of Cohorts Associated with Persistence Analyses

Total Enrolled	Total Enrolled - Persistence	Total Cohort at Month X	ATP Cohort for Persistence MenC at Month X	ATP Cohort for Persistence MenAWY at Month X
Enrolled in study regardless of visit when enrolled.	Any titer at any time point.	All MenACWY-TT-027 vaccinated subjects who return for Month X	MenC result at Month X available	
	Enrollment or lack of enrollment in MenACWY-TT-100 is not exclusionary	Persistence data available	Eligible for MenACWY-TT-027	Eligible for MenACWY-TT-027

MenACWY-TT-100 (C0921004)

Table 1. Summary Description of Cohorts Associated with Persistence Analyses

Total Enrolled	Total Enrolled - Persistence	Total Cohort at Month X	ATP Cohort for Persistence MenC at Month X	ATP Cohort for Persistence MenAWY at Month X
			Vaccinated in MenACWY-TT-027 with assigned vaccine	Vaccinated in MenACWY-TT-027 with assigned vaccine
			No unplanned meningococcal vaccines before Month X	No unplanned meningococcal vaccines before Month X, except MenC vaccine in response to suboptimal response in MenC from MenACWY-TT-027
			No meningococcal history before Month X	No meningococcal history before Month X
			Comply with blood sampling interval for Month X	Comply with blood sampling interval for Month X
			No immuno- compromising medical condition	No immuno- compromising medical condition
			No immuno- suppressants, etc.	No immuno- suppressants, etc.
			Not excluded from ATP in MenACWY-TT-027 and not excluded from previous ATP persistence cohorts, unless reason for exclusion is either missed windows or no immunogenicity results.	Not excluded from ATP in MenACWY-TT-027 and not excluded from previous ATP persistence cohorts, unless reason for exclusion is either (1) missed windows or (2) no immunogenicity results or (3)revaccination with monovalent MenC due to suboptimal MenC response in MenACWY-TT-027

MenACWY-TT-100 (C0921004)

Table 1. Summary Description of Cohorts Associated with Persistence Analyses

Total Enrolled	Total Enrolled - Persistence	Total Cohort at Month X	ATP Cohort for Persistence MenC at	ATP Cohort for Persistence
			Month X	MenAWY at
				Month X
			Medications/products/	Medications/
			vaccines and/or no	products/vaccines
			intercurrent medical	and/or no

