8. STATISTICAL CALCULATIONS

8.1. Derived and Transformed Data

- Age in years will be calculated as (date minus date of birth)/365.25, rounded down to nearest integer.
- Duration from primary vaccination to any persistence time point will use day of primary vaccination as Day 0. Duration from booster will use day of booster vaccination as Day 0.
- Activity date is defined as the date associated with any activity performed at indicated visit.
- For a given subject and a given immunogenicity measurement, missing or non-evaluable measurements will not be replaced. Therefore, an analysis will exclude subjects with missing or non-evaluable measurements.
- The cutoff values for the assays are defined by the laboratory before the analysis and are described in Section 5.7.3 of the protocol.

MenACWY-TT-100 (C0921004)

- A seronegative subject is a subject whose titer is below the cutoff value.
- A seropositive subject is a subject whose titer is greater than or equal to the cutoff value.
- GMTs are calculated by taking the antilog of the mean of the log titer transformations. Antibody titers below the cutoff value of the assay will be given an arbitrary value of half the cutoff value for the purpose of the GMT calculation.
- rSBA vaccine response for groups A, C, W-135, and Y after the booster dose is defined as:
 - For initially seronegative subjects (pre-vaccination titer <1:8): rSBA antibody titers ≥1:32 1 month after vaccination, and
 - For initially seropositive subjects (pre-vaccination titer ≥1:8): a 4-fold increase in rSBA antibody titers 1 month after vaccination.
- hSBA vaccine response for groups A, C, W-135, and Y after the booster dose is defined as:
 - For initially seronegative subjects (pre-vaccination hSBA titer <1:4): hSBA antibody titers ≥1:8 1 month after vaccination, and
 - For initially seropositive subjects (pre-vaccination hSBA titer ≥1:4): a 4-fold increase in hSBA antibody titers 1 month after vaccination.
- For subjects who received MenC vaccine because they were suboptimal responders during the persistence phase of the MenACWY-TT-027 study, all subsequent persistence results for MenC will be replaced by half the cutoff in order to reflect the immunogenicity of the subjects, had they not been revaccinated. This includes Month 126. However, there will be no adjustment to postbooster MenC titers.

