10. CHANGES FROM PLANNED ANALYSES

Please note that the changes from planned analyses to be included in the clinical study report (CSR) will be identified during the CSR review.

- The adapted ATP cohort and total enrolled cohort have been added and are explained in detail.
- Analysis of persistence for all the antigens MenA, MenC, MenW-135, and MenY will be done using the ATP cohort for persistence at Month X which will include those subjects who received a booster dose of MenC vaccine because they were non-responders after the primary vaccination in Study MenACWY-TT-027. A decision was made to include the results of the subjects who were administered a booster dose of MenC vaccine, since the removal of the results of these subjects from the analysis for persistence of MenC would result in the over estimation of the persistence of MenC.
- The new statement is "who have available assay results for at least 1 of 3 antigens (MenA or MenW-135 or MenY) at Month X." has been modified to "who have available assay results for at least 1 of 3 antigens (MenA or MenW-135 or MenY) or for MenC (for subjects who had not received MenC vaccine because they were non-responders during the persistence phase of Study MenACWY-TT-027 please see Section 7.1 of the SAP) at Month X".

MenACWY-TT-100 (C0921004)

For subjects who received MenC vaccine because they were suboptimal responders during the persistence phase of the MenACWY-TT-027 study, the persistence results for MenC will be replaced by half the cutoff in order to reflect the immunogenicity of the subjects, had they not been revaccinated.

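### SAP Table 1 and the last bullet of 6.1.2 contradict the SAP's own rule that MenC-revaccinated subjects stay in the MenC ATP persistence cohort

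*SAP*

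**What the plan says.** The intended rule appears in several places in the SAP.

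- Section 10 declares a change from the protocol. Persistence of all four antigens, MenC included, is analysed on an ATP cohort that contains subjects given MenC vaccine for non-response, "since the removal of the results of these subjects from the analysis for persistence of MenC would result in the over estimation" of MenC persistence.
- Section 8.1 fixes their values: "all subsequent persistence results for MenC will be replaced by half the cutoff". Month 126 is included.
- Section 6.1.2 opens by giving the two ATP persistence cohorts common requirements: "The requirements for both cohorts are the same except that membership in the MenC (or MenAWY) cohort requires at least one MenC" (or MenAWY) titer. Its vaccine bullet bars unplanned meningococcal vaccines "with the exception of subjects who received the MenC vaccine because they were suboptimal responders during the persistence phase of Study MenACWY-TT-027".

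Other current text in the SAP says something different.

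- Table 1, MenAWY column, has the exception twice: "No unplanned meningococcal vaccines before Month X, except MenC vaccine in response to suboptimal response in MenC from MenACWY-TT-027", and a third waiver of earlier ATP exclusions, "3)revaccination with monovalent MenC due to suboptimal MenC response in MenACWY-TT-027".
- Table 1, MenC column, bars unplanned meningococcal vaccines with no exception. It waives earlier ATP exclusions only under the condition "unless reason for exclusion is either missed windows or no immunogenicity results".
- The last bullet of 6.1.2, which serves both cohorts, waives only missed sampling windows and a "lack of availability of immunogenicity results at a previous time point".

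**The concern.** A programmer working from Table 1 and one working from Section 10, 8.1 and the vaccine bullet of 6.1.2 would build different cohorts for rSBA-MenC. That is a primary endpoint, and MenC is the only serogroup compared between ACWY<2 and MenCCRM. The MenC column still matches protocol 10.4.1.2, the rule that Section 10 says was changed. The departure from the protocol is declared and is not the error. The error is that these parts of the SAP were not brought into line with it.

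If Table 1 is followed, the replacement rule in 8.1 has no effect in the ATP analysis, and the estimates move in the direction Section 10 set out to avoid. The longitudinal model in 7.1.3 also takes its Month 78 to 126 data from the ATP persistence cohorts.

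**Working it through.** **Texts side by side**

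| Requirement | Table 1, MenC | Table 1, MenAWY | SAP 6.1.2, both cohorts |
|---|---|---|---|
| Unplanned meningococcal vaccine | no exception | MenC revaccination excepted | MenC revaccination excepted |
| Earlier ATP exclusion waived for | windows, missing results | windows, missing results, MenC revaccination | windows, missing results |

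The two Table 1 columns differ by more than the titer. On earlier exclusions, 6.1.2 agrees with the MenC column but not with the MenAWY column or with protocol 10.4.1.3, which also waives MenC revaccination.

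**Direction.** The rSBA cutoff is 1:8 (protocol 5.7.3), so half the cutoff is 1:4. A retained revaccinee therefore fails both the 1:8 and the 1:128 threshold. Dropping such subjects removes only failures. The percentage rises whenever at least one is dropped and the rate is above zero. The GMT rises unless all other titers are also 1:4.

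**Inputs for size**

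- Planned group sizes by year: protocol 10.3.
- MenC rates: 77.6% (ACWY<2) and 90.8% (ACWY≥2), the Year 5 figures for detectable antibody in protocol 1.2. Using them as rates at 1:8 is an assumption.
- Revaccinated share r: not in the documents, so assumed.
- The plan states no figure for this shift. As a check on the interval method, 146/183 gives an exact interval of 73.2 to 85.3, which matches Table 17 at 80%.

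**Percentage.** Let p be the rate among the rest. Table 1 reports p; the Section 10 rule reports p × (1 − r). With r = 18/183 = 9.84%:

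- p = 77.6%: 77.6 × 0.9016 = 70.0%, a gap of 7.6 points.
- p = 50%: 45.1%, a gap of 4.9 points.
- p = 90.8%: 81.9%, a gap of 8.9 points.
- If 77.6% already includes the revaccinees: 77.6 / 0.9016 = 86.1%, a gap of 8.5 points.

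**GMT.** The inflation factor is (G/4)^r, with G the GMT among the rest. For an assumed G of 30, 7.5^0.0984 = 1.22. For an assumed G of 100, 25^0.0984 = 1.37.

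**The 10% trigger (SAP 7.1.2).** A second analysis on the total enrolled cohort runs if exclusions of all kinds exceed 10% in any group at any time point. At planned sizes, the largest counts that do not trigger it are:

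| Year | ACWY groups | MenCCRM, MenPS |
|---|---|---|
| 6 | 18/183 | 6/61 |
| 7 | 16/165 | 5/55 |
| 8 | 15/150 | 5/50 |
| 9 | 13/135 | 4/45 |
| 10 | 12/122 | 4/41 |

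Other exclusions use up part of this room. With N = 183, p = 77.6%, o other exclusions and k revaccinees, r = k/(183 − o):

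| o (assumed share) | largest k | r | Section 10 rule | gap, points |
|---|---|---|---|---|
| 4 (2%) | 14 | 7.82% | 71.5% | 6.1 |
| 9 (5%) | 9 | 5.17% | 73.6% | 4.0 |
| 15 (8%) | 3 | 1.79% | 76.2% | 1.4 |

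**Scale.** The exact 95% interval near 77.6% is 70.9 to 83.4 for N = 183 (half-width 6.3 points) and 64.5 to 86.8 for N = 61 (half-width 11.2).

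**Booster cohorts.** SAP 6.2.2 admits to the booster ATP safety cohort only subjects not excluded from either Month 126 ATP cohort, apart from windows or missing results. Under Table 1, revaccinees are excluded from the MenC one. They would then leave the booster safety cohort and with it the booster MenAWY cohort, although 6.2.4 and Table 3 say monovalent MenC revaccination does not exclude them there.

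**The case against.** The strongest reply is that the governing rule is already clear. Section 10, 8.1 and the vaccine bullet of 6.1.2 agree, and Table 1 is a summary that sends the reader to 6.1.2. An analyst would have to prefer a summary cell over three fuller statements. That is fair, and it makes the right correction easy to identify. It does not settle which text a programmer will use: the SAP gives no order of precedence, and the last bullet of 6.1.2 is itself detailed text.

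Several limits stand:

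- The last bullet matters only if an earlier ATP cohort excluded someone for revaccination. Protocol 10.4.1.3 shows that this was foreseen, not that it happened.
- That bullet and Table 1 cannot both govern the MenAWY persistence cohort, because the MenAWY column has the waiver. The two routes to harm there are alternatives.
- The 18/183 case is a ceiling. Each revaccinee moves the result by about 0.776/183 = 0.42 points, so two move it by about 0.8, well inside the interval half-width.
- Higher revaccination rates trigger the second analysis, although that only complements the ATP result.
- The analyses are descriptive, and the ACWY<2 versus MenCCRM difference moves materially only if revaccination rates differ between the groups.
- Primary booster safety uses the booster total vaccinated cohort and is unaffected. Revaccinees are outside the booster MenC cohort by design.

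**Conclusion.** The concern holds and should be fixed. The Table 1 contradiction is certain from the text. The last-bullet contradiction is also real, but its effect is conditional. Used as the cohort specification, Table 1 would raise MenC percentages and GMTs relative to the SAP's stated target, which is the result had these subjects not been revaccinated.

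The direction is certain if anyone was revaccinated; the size is not known. Under the assumptions above, an ACWY<2 estimate near 77.6% could be up to 7.6 points too high without triggering the second analysis, or 8.5 points if 77.6% already includes revaccinees. The gap would be 1.4 to 6.1 points once other exclusions take 8 to 2% of the group. With no revaccinees there is no effect.

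The assay-result bullet of 6.1.2 is a separate wording defect. It is ambiguous about revaccinees and points to 7.1, while the replacement rule is in 8.1. It does not by itself exclude a revaccinee who has a MenA, W-135 or Y result, and no bias is claimed for it.

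**What to change.** Apply the Section 10 rule throughout the SAP:

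1. Add the MenC-revaccination exception to both MenC cells of Table 1 (unplanned vaccine and earlier ATP exclusion).
2. Add the same waiver to the last bullet of 6.1.2.
3. Reword the assay-result bullet of 6.1.2 so that revaccinees' MenC results count as set out in 8.1, and change its cross-reference from 7.1 to 8.1.
4. Confirm that 6.2.2 and the Year 10 cell of Table 3 do not treat MenC revaccination as an exclusion for the booster MenAWY cohort.

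Optionally, report the number of revaccinees by group and time point, with one MenC table that leaves them out. The required changes are SAP wording only: two table cells, two bullets, one cross-reference and one check. They need no new data and no new table.

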- Administration of a meningococcal vaccine of any serogroup not foreseen by the study protocol at any time during the study period.
- Immunoglobulins and/or any blood products administered during the study period.
- Drug and/or alcohol abuse.

A detailed, comprehensive list of reasons for elimination from ATP analyses will be established at the time of data cleaning.

6.6. Intercurrent medical conditions that may lead to elimination of a subject from ATP analyses

At each study visit subsequent to the vaccination visit, it must be verified if the subject has experienced or is experiencing any intercurrent medical condition. If it is the case, the condition(s) must be recorded in the eCRF.

The following may result in the elimination of subjects from the ATP cohort for immunogenicity, but not necessarily from the study:

- Occurrence of meningococcal disease*.
- Any confirmed or suspected condition that has the capability of altering the subject's immune response (e.g. intercurrent lymphopenia).
- Any confirmed or suspected immunosuppressive or immunodeficient condition, including Human immunodeficiency virus (HIV) infection based on medical history and physical examination (no laboratory testing required).

- Diagnosis of any serious chronic illness.
- * Occurrence of meningococcal disease should be recorded as an SAE.

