10.4.1.2. According-To-Protocol (ATP) cohort for persistence – MenC at Month X

Analysis of persistence of MenC antibody titres for Month X will be done on ATP cohort for persistence – MenC at Month X. The ATP cohort for antibody persistence – MenC at Month X will include all evaluable subjects:

- who were eligible in study MenACWY-TT-027 (108658).
- who have received the primary vaccination with MenACWY-TT or *Meningitec* or *Mencevax ACWY* during study MenACWY-TT-027 (108658) according to their treatment group.
- who have available assay results for MenC antigen at Month X.
- who have not received a meningococcal vaccine not planned in protocol MenACWY-TT-027 (108658) before Month X.
- who do not have a history of meningococcal disease prior to Month X.
- who comply with the blood sampling intervals defined in Table 5 for Month X.
- who do not have an immunocompromising medical condition.
- who have not received any immunosuppressant(s) or other immune-modifying drug(s), immunoglobulins, any blood products, investigational drugs, and/or investigational vaccines within 30 days of persistence blood sample.
- who were not excluded from the ATP cohort in the primary study MenACWY-TT-027
 (108658) and from the previous ATP persistence cohorts, unless the reason for exclusion
 was either non-compliance with the protocol-defined serum sampling windows or a lack of
 availability of immunogenicity results at previous time point

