10.4.1.3. According-To-Protocol (ATP) cohort for persistence – MenAWY at Month X

Analysis of persistence of MenA, W-135 and Y antibody titres at Month X will be done on the ATP cohort for persistence – MenAWY at Month X. The ATP cohort for persistence Month X – MenAWY will include all evaluable subjects:

• who were eligible in study MenACWY-TT-027 (108658).

- who have received the primary vaccination with MenACWY-TT or *Meningitec* or *Mencevax ACWY* during study MenACWY-TT-027 (108658) according to their treatment group.
- who have available assay results for at least one of three antigens (MenA or W-135 or MenY) at Month X.
- who have not received a meningococcal vaccine not planned in protocol MenACWY-TT-027 (108658) before Month X with the exception of a monovalent MenC conjugate vaccine because of suboptimal response to *N. meningitidis* serogroup C after vaccination in the primary study MenACWY-TT-027 (108568).
- who do not have a history of meningococcal disease prior to Month X.
- who comply with the blood sampling intervals defined in Table 5 for Month X.
- who do not have an immunocompromising medical condition.
- who have not received any immunosuppressant(s) or other immune-modifying drug(s), immunoglobulins, any blood products, investigational drugs, and/or investigational vaccines within 30 days of persistence blood sample.
- who were not excluded from the ATP cohort in the primary study MenACWY-TT-027 (108658) and from the previous ATP persistence cohorts, unless the reason for exclusion was either non-compliance with the protocol-defined serum sampling windows or a lack of availability of immunogenicity results at previous time point or re-vaccination with a monovalent meningococcal polysaccharide conjugate vaccine of serogroup C due to suboptimal response to *N. meningitidis* serogroup C after vaccination in the primary study MenACWY-TT-027 (108658).

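### SAP 6.1.2, Table 1 and 6.2.2 drop MenC-revaccinated subjects from ATP cohorts in which SAP 8.1, 10 and 6.2.4 keep them

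*SAP*

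**What the plan says.** SAP 6.1.2 defines two persistence ATP cohorts per visit, MenC and MenAWY, and states that their requirements differ only in which titre must be available. Its vaccine bullet exempts subjects given MenC vaccine as suboptimal responders. Its last bullet carries earlier exclusions forward, "and from the previous ATP persistence cohorts, unless the reason for exclusion was either non-compliance with the protocol-defined serum sampling windows". The only other exception there is an earlier visit without results. It has no third exception.

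Protocol 10.4.1.3 (MenAWY) has a third exception: "or re-vaccination with a monovalent meningococcal polysaccharide conjugate vaccine of serogroup C". SAP Table 1 has it in the MenAWY column: "3)revaccination with monovalent MenC due to suboptimal MenC response in MenACWY-TT-027". In Table 1's MenC column the carry-forward row stops at two: "not excluded from previous ATP persistence cohorts, unless reason for exclusion is either missed windows or no immunogenicity results". The vaccine row of that column allows no exception either.

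SAP section 10 says that the persistence analysis of all four serogroups includes the revaccinated subjects, since leaving them out would overestimate MenC persistence. SAP 8.1 sets their later MenC persistence results, Month 126 included, to half the cutoff.

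SAP 6.2.2 admits to the booster ATP safety cohort only subjects excluded from neither Month 126 persistence ATP cohort, apart from window or missing-result reasons. SAP 6.2.3 and 6.2.4 draw both booster immunogenicity cohorts from it. SAP 6.2.4 states that prior monovalent MenC revaccination does not bar a subject from the MenAWY cohort.

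On medication, SAP 6.1.2 excludes for immunosuppressants, immune-modifying drugs, immunoglobulins, blood products, "investigational drugs, and/or investigational vaccines within 30 days of the persistence blood sample". Table 1 also applies protocol 6.5.2, which lists, among others, "Immunoglobulins and/or any blood products administered during the study period".

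**The concern.** The cohort definitions are what a programmer codes, and on revaccinated subjects they give different answers. These subjects were revaccinated because their MenC response was poor. Removing them from the MenC denominator raises the reported persistence, which is the bias that section 10 was written to prevent. Comparisons of ACWY<2 with MenCCRM and of ACWY≥2 with MenPS would also shift if revaccination was more frequent in one arm. In the booster phase, subjects whose MenA, MenW-135 and MenY results are valid would be lost for a reason that concerns MenC alone.

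The choice also affects the check in SAP 7.1.2. Exclusions are counted separately for the MenC and MenAWY cohorts, so whether a second analysis is triggered can depend on which rule was coded.

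A lesser issue is that the 30-day medication criterion is tied to one blood sample, yet an exclusion under it carries to every later visit. The two reasons that do not carry forward are also tied to a single visit.

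**Working it through.** **The rules side by side.** Is MenC revaccination exempt?

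| Place | Cohort | Vaccine criterion | Carry-forward criterion |
|---|---|---|---|
| Protocol 10.4.1.2 | MenC | no | no |
| Protocol 10.4.1.3 | MenAWY | yes | yes |
| SAP 6.1.2 | both | yes | no |
| SAP Table 1 | MenC | no | no |
| SAP Table 1 | MenAWY | yes | yes |
| SAP 8.1 and 10 | all four serogroups | subjects kept, MenC at half the cutoff | subjects kept |

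Table 1's MenC column still carries the protocol rule that section 10 replaced. SAP 6.1.2 was updated in the vaccine bullet but not in the carry-forward bullet.

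**One revaccinated subject followed through.**
1. Table 1, MenC column: fails the vaccine row at Month 78 and at each later visit.
2. SAP 6.1.2: passes the vaccine bullet, but fails carry-forward if an earlier ATP cohort excluded the subject for revaccination. The bullet does not separate MenC from MenAWY, so a MenC exclusion at Month 78 under Table 1 would also count against MenAWY at Month 90.
3. SAP 6.2.2: exclusion from one Month 126 cohort is enough. The subject leaves the booster ATP safety cohort.
4. SAP 6.2.4: membership of that cohort is required, so the subject leaves booster MenAWY, although the same section says that inclusion is possible.

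**Size of the MenC effect.** Let f be the share revaccinated and p the percentage of the others with rSBA-MenC of at least 1:8. Half the cutoff is 1:4, so a retained revaccinated subject counts as below 1:8.
- Kept: (1 − f) × p. Dropped: p. Overstatement: f × p.
- With p = 80% (a row of protocol Table 17) and f assumed: f = 1% gives 0.8 points, 2% gives 1.6, and 5% gives 4.0.
- If the excluded share is exactly 10%, all of it revaccinated, no second analysis is required. The overstatement is then 80 − 0.90 × 80 = 8.0 points.

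**The medication criterion.** Planned numbers come from protocol 10.3. Taking 10% off per visit and rounding up gives 183, 165, 149, 135, 122 and 61, 55, 50, 45, 41. The plan prints 150 at Year 8 and otherwise agrees. Table 17's Clopper-Pearson rows checked at N = 122 and 41 also reproduce: at 80%, 72.2 to 87.0 and 65.1 to 91.2.

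Let q be the assumed share with a new 30-day reason at each visit, independent across visits. The share already excluded on reaching Month 126, from Months 78 to 114, is 1 − (1 − q)^4.
- q = 1%: 1 − 0.99^4 = 3.9%, or 4.8 of 122 and 1.6 of 41.
- q = 2%: 1 − 0.98^4 = 7.8%, or 9.5 of 122 and 3.2 of 41.

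Adding Month 126 itself gives 4.9% and 9.6%, against 1% and 2% if the reason applied only to its own visit. At q = 2% about 110 of 122 and 37 of 41 remain. The 80% interval then widens from 14.8 to 15.7 points (71.3 to 87.0) and from 26.1 to 27.2 points (64.8 to 92.0).

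**The case against.** On revaccination, the best defence is that the intent is plain. The vaccine bullet of 6.1.2 exempts these subjects, 8.1 says how their titres are handled, section 10 says why they stay, and Table 1 is only a summary. Within the 6.1.2 text alone, the gap matters only if an earlier ATP cohort excluded a subject for revaccination, and the cohort definitions of studies 028 to 032 are not in the documents. That stands: renewed overestimation is not certain. It does not remove the contradiction. Table 1's MenC column excludes these subjects at Month 78 without reference to any earlier study, and 6.2.2 then conflicts with 6.2.4. Protocol 10.4.1.3 also shows that exclusion for revaccination was expected, since it makes an exception for it.

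On medication, a reader might infer that the plan regards these exposures as over after 30 days, so that the carry-forward list is simply too short. The documents do not support this. The protocol has the same rule, "and from the previous ATP persistence cohorts, unless the reason for exclusion", so the SAP does not depart from it. Protocol 6.5.2 can also eliminate a subject for chronic immunosuppressants, blood products or investigational products over the whole study period. Nor do the 30-day rule and 6.5.2 necessarily define two rival cohorts. They can be applied together, since 6.5.2 says only that use may affect evaluability and leaves the full list of reasons to data cleaning.

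A reader might also extend the accumulation to studies 028 to 032 and obtain a much larger loss. That needs those studies to have used the same criterion, which cannot be checked here. A loss above 10% in a group would in any case trigger the second analysis.

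**Conclusion.** The revaccination contradiction is established from the text and needs no assumed rate. SAP 6.1.2 and Table 1 cannot both be followed with 8.1 and 10, nor 6.2.2 and Table 1's MenC column with 6.2.4. The size of any bias is unknown because the documents do not count the revaccinated subjects. The 0.8 to 4.0 points rest on an assumed share of 1% to 5% and on 80% of the others reaching 1:8.

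The medication point is a low-priority design matter. The 4% to 8% by Month 126 assumes 1% to 2% new exposures per visit, independence, attendance at every visit and the four earlier visits of this study only. Entry criteria that exclude immunodeficiency and serious chronic illness argue for a low rate. Repeat exposure in the same subjects would lower the total, as would skipped visits.

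Both points touch ATP analyses only. All analyses are descriptive, primary booster safety uses the booster total vaccinated cohort, and a complementary immunogenicity analysis runs if exclusions exceed 10% in any group. Below that trigger no back-up analysis is required.

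**What to change.** 1. In the SAP 6.1.2 carry-forward bullet, add monovalent MenC revaccination for suboptimal response, handled under SAP 8.1, as a third exception.
2. In Table 1, put the same exception in the vaccine row and the carry-forward row of the MenC column.
3. In SAP 6.2.2, add it to the reasons for Month 126 exclusion that do not bar a subject from the booster ATP safety cohort. Leave the separate exclusion from the booster MenC cohort in 6.2.3 as it is.
4. Record the 6.2.2 change in SAP section 10, since protocol 10.4.2.2 has no such exception.
5. Optional: let a 30-day medication exclusion lapse at later visits where it was the only reason, and state how it combines with protocol 6.5.2. Both must be settled together, because an exception in 6.1.2 alone would leave 6.5.2 able to exclude some of the same subjects. SAP wording should not quietly override a protocol section.

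Items 1 to 4 cost SAP wording and cohort programming. The drawback is that ATP membership may differ slightly from that in annex reports already issued for earlier time points, which needs a footnote.
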